9.4. SERIOUS AND UNANTICIPATED ADVERSE DEVICE EFFECTS

A serious and unanticipated adverse device effect is defined as “any serious adverse effect on health or safety or any life-threatening problem or death caused by, or associated with, a device if that effect, problem, or death was not previously identified in nature, severity, or degree of incidence in the investigational plan, or any other unanticipated serious problem associated with a device that relates to the rights, safety or welfare of subjects.”

9.5. ADVERSE EVENT REPORTING

All AEs that occur during the course of the study must be reported on the Adverse Event CRF. The Investigator must determine the intensity of the event.

| | |
|-----------------|--|
| Mild | Awareness of sign or symptom, but easily tolerated |
| Moderate | Discomfort enough to cause interference with normal daily activities |
| Severe | Inability to perform normal daily activities |

All SAEs and adverse device effects (ADEs) must be reported by the Investigator to Allergan in writing within 24 hours from the point in time when the Investigator becomes aware of the event.

It is the responsibility of the Investigator to promptly notify the Ethics Committee (EC) of all SAEs and unanticipated problems, per the ECs reporting requirements.

Throughout the course of the proposed study, all efforts will be made to remain alert to possible adverse experiences or untoward findings. If adverse experiences occur, the first concern will be the safety and welfare of the participant. Appropriate medical intervention will be made.

The Sponsor will immediately conduct an evaluation of any unanticipated adverse device effect. If it is determined by the Sponsor to present an unreasonable risk to study participants, all investigations or parts of the investigation presenting that risk will be terminated as soon as possible. Termination will occur not later than five working days after the Sponsor makes this determination, and not later than 15 working days after first receiving notice of the event. The Sponsor will not resume an investigation terminated under these conditions without an additional EC approval.

Contact information for reporting Serious Adverse Events:

| Sponsor Contact Information for reporting Serious Adverse Events | |
|--|------------|
| Allergan: [Redacted] | |
| ADDITIONALLY please send a copy to: [Redacted] | |
| [Redacted] | [Redacted] |
| [Redacted] | [Redacted] |
| [Redacted] | [Redacted] |
| [Redacted] | [Redacted] |
| [Redacted] | [Redacted] |
| [Redacted] | [Redacted] |

9.6. ANTICIPATED ADVERSE EVENTS

The following is a list of potential AEs associated with the use of the device:

- Nasal discomfort or pain
- Epistaxis
- Excessive sneezing
- Nasal irritation, paresthesia or numbness post-stimulation
- Nasal infection, abrasion or inflammation

- Skin irritation or hypersensitivity
- Headache (e.g., tension, migraine, etc.)
- Facial pain
- Excessive salivation
- Sensation of teeth vibrating
- Excessive rhinorrhea
- Temporary aggravation of nasal allergies
- Allergic reaction to contact materials

The following is a list of potential AEs associated with the testing procedures at Screening:

- Ocular discomfort
- Moderate or severe conjunctival injection
- Clinically significant decrease in visual acuity
- Clinically significant increase in corneal or conjunctival epithelial defects
- With use of proxytacaine, temporary burning, stinging and conjunctival redness of the eyes
- With use of proxytacaine, a rare hyperallergic corneal reaction characterized by epithelial keratitis, sloughing of epithelium, corneal filaments and iritis
- With the Schirmer test, corneal irritation and abrasion
- Allergic reaction to contact materials

10. PREGNANCY

Women of Childbearing Potential (WOCBP) include any females who have experienced menarche and who have not undergone successful surgical sterilization (hysterectomy, bilateral tubal ligation or bilateral oophorectomy) or are not postmenopausal at least 12 months since last menses. WOCBP will be required to use designated methods of birth control during the course of the study. All women who are pregnant, nursing an infant, or planning a pregnancy will be excluded from participation.

If a participant or Investigator suspects that the participant may be pregnant prior to study device administration, the study device must be withheld until the results of pregnancy testing are available. If pregnancy is confirmed, the participant must not administer the study device and must not be enrolled in the study.

11. STATISTICAL HYPOTHESIS AND METHODS OF ANALYSES

11.1. POWER CALCULATION AND DETERMINATION OF SAMPLE SIZE

Approximately 35 completed participants will be enrolled. This is an exploratory study and no formal sample size calculation was performed. The results from this study may be used to determine the appropriate time points and power for future studies.

11.2. STATISTICAL HYPOTHESES AND LEVEL OF SIGNIFICANCE

The null hypothesis for each of the exploratory parameters is the difference in the change from the pre-application value at each post-application time point between the intranasal (test) and extranasal (control) applications are zero.

The alternative hypothesis for each of the exploratory parameters is the difference in the change from the pre-application value at each post-application time point between the intranasal (test) and extranasal (control) applications are not zero.

The hypothesis can be expressed as:

$$H_0: \Delta = 0$$

$$H_A: \Delta \neq 0 \text{ mm}$$

where Δ represents the difference between applications for the change from the pre-application value and each post-application time point. Statistical tests will be two-sided and evaluated at an α of 0.05.

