2. STUDY OBJECTIVES

The primary objective of this study is to compare the change in tear meniscus height (TMH) (immediately post versus pre-application) produced by intranasal application of TrueTear (test) versus the same device applied extranasally (control). In addition, this study will also:

- Compare the duration of change in TMH (post versus pre-application) produced by intranasal (test) versus extranasal (control) application of TrueTear
- Compare the change and duration of change (post versus pre-application) in lipid layer thickness (LLT) produced by intranasal (test) versus extranasal (control) application of TrueTear
- Compare the change and duration of change (post versus pre-application) in non-invasive tear film break-up time (NITBUT), protective index and exposed area produced by intranasal (test) versus extranasal (control) application of TrueTear

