3. CLINICAL HYPOTHESES

The clinical hypothesis for this study is that the difference in TMH measured pre-application and immediately post-application in the study eye between the two applications (intranasal vs extranasal control) will be statistically significantly greater in favor of intranasal stimulation.

Additionally, the difference in the change of the lipid layer thickness measured pre-application and immediately post-application in the study eye between the two applications (intranasal vs extranasal control) will be statistically significantly greater in favor of intranasal stimulation.

[figure not shown]

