11.3. RANDOMIZATION

Each participant will be treated with the active and control applications. The sequence of the applications will be randomly assigned using a computer-generated randomization schedule. Participants will be randomly assigned to one of two application sequences:

A. Intranasal: Extranasal

B. Extranasal: Intranasal

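### If the change defined in section 11.2 is analysed without adjustment, entering each visit's pre-application reading as a within-participant covariate could gain precision for one degree of freedom; the size of the gain is unknown and may be nil

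*Combined protocol and SAP*

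**What the plan says.** Section 11.2 sets null and alternative hypotheses for each exploratory parameter. Delta is the "difference between applications for the change from the pre-application value and each post-application time point", and "Statistical tests will be two-sided and evaluated at an α of 0.05". Section 2 frames the primary objective as a comparison of change in tear meniscus height (TMH). Section 3 does the same, referring to the "difference in TMH measured pre-application and immediately post-application in the study eye between the two applications". A pre-application reading therefore exists for each application.

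The design is a two-period crossover: "Each participant will be treated with the active and control applications" (11.3). On size, 11.1 says "Approximately 35 completed participants will be enrolled" and "This is an exploratory study and no formal sample size calculation was performed".

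No visible text names a test, a model or a covariate. The table of contents lists 11.8 as the effectiveness analyses, but the text after 11.7 is blacked out.

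**The concern.** A crossover already removes stable differences between people. Subtracting the pre-application reading at each visit can then only help with visit-to-visit variation, and it brings two further readings, each with its own noise, into the contrast. If post-application values follow that day's pre-application value only loosely, as they may after an acute stimulus, a coefficient fixed at 1 over-corrects. Estimating the coefficient avoids this.

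What is at stake is precision, not bias. The trial has about 35 pairs and no power calculation. Section 11.1 says the results may inform time points and power for later studies. The duration objective depends on whether small residual effects can be seen at late time points. Wider intervals than necessary weaken both uses.

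**Working it through.** **Inputs from the documents.** Two-period crossover with two sequences (11.3); n = 35 completers (11.1), which agrees with the two phases, 10 + 25 = 35; two-sided alpha of 0.05 (11.2). There is no stated power, SD or effect size to reproduce.

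**Assumed, because the documents give neither.** r is the same-visit pre/post correlation after removing the participant effect. k is the post SD divided by the pre SD. The order is randomised and carryover into the second pre-application reading is taken as nil, so adjusted and unadjusted analyses target the same delta.

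**Variance per visit, in units of the pre-application variance**
- Unadjusted change: k² + 1 − 2rk
- Post value alone: k²
- Adjusted for the pre-application reading: k²(1 − r²)

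The excess of unadjusted over adjusted is (k² + 1 − 2rk) − k²(1 − r²) = (1 − rk)². This is never negative, and it is zero when rk = 1. For k = 1 the ratio of adjusted to unadjusted is (1 − r²)/(2 − 2r) = (1 + r)/2.

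**Cost of estimating the slope at n = 35.** Multiply by 1 + 1/(n − 4) = 32/31 = 1.032. Residual degrees of freedom fall from 33 to 32.

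**Results for k = 1.** The fourth column is 35 × ratio: the number of participants with which the adjusted analysis matches the unadjusted analysis of 35. The last column sets the true effect so that unadjusted change has 80% power. That is a benchmark, not a figure from the plan.

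| r | (1 + r)/2 | × 32/31 | Equivalent n | Power, from 80% |
|---|---|---|---|---|
| 0 | 0.50 | 0.52 | 18.1 | 97% |
| 0.3 | 0.65 | 0.67 | 23.5 | 93% |
| 0.5 | 0.75 | 0.77 | 27.1 | 89% |
| 0.7 | 0.85 | 0.88 | 30.7 | 85% |
| 0.9 | 0.95 | 0.98 | 34.3 | 81% |

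At r = 0.5 the confidence interval is about 12% narrower. Simulation with an 18/17 sequence split and a period term agrees with these ratios to within about 0.02.

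**Results when post values are more variable than pre values (same formula, with the 32/31 factor)**
- k = 1.5: 0.90, 0.995 and 1.03 for r = 0.3, 0.5 and 0.7.
- k = 2: 0.83, 0.99, 1.03 and 0.96 for r = 0, 0.3, 0.5 and 0.7.

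At k = 2, r = 0.5: unadjusted 4 + 1 − 2 = 3; adjusted 4 × 0.75 = 3; ratio 1 × 1.032 = 1.03. This is the case rk = 1, where adjustment costs about 3% and gains nothing.

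**Does a hypothesis on change rule out adjustment?** No. Regressing change on the pre-application covariate gives the same treatment estimate as regressing the post value on it; in simulation the two differed by less than 1e-14.

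**The case against.** The strongest reply is that 11.2 states a hypothesis and names no estimator. Delta as written can be estimated with or without a covariate, and the section that would say which is redacted. This stands. A reader might infer that the plan uses an unadjusted change score, or that 11.2 defines the wrong quantity. The documents support neither reading: what is blacked out is not missing from the plan, and randomised order means that an adjusted model estimates the same delta.

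A reader might also infer that change is efficient only when pre and post readings are almost perfectly correlated, or that it is always noisier than the post value alone when r is below 0.5. Both hold only for k = 1. The general conditions are rk = 1 and rk < 0.5, so at k = 2 the second threshold is r = 0.25. Nothing in the documents fixes k at 1, and stimulation may widen the spread of post values, particularly at the immediate time point. Equal SDs are more plausible later, as the response fades.

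Finally, the study is exploratory with no power target, so no stated figure becomes wrong, and an unadjusted contrast of change would be valid. That also stands. It limits the point to efficiency but does not remove it, because later studies are to draw on these estimates.

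**Conclusion.** The point holds as a conditional improvement in efficiency. If the redacted model leaves the pre-application reading unadjusted, adjusting for it would reduce the variance of the treatment contrast by up to about half (k = 1, r = 0) and by about 23% at k = 1, r = 0.5. It would give nothing, or a loss of about 3%, where rk is near 1. The documents do not place the trial within that range, and it may differ between TMH, lipid layer thickness and the break-up measures, and between time points.

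The figures rest on 35 complete pairs, roughly normal data, the assumed values of r and k, and no carryover into the second pre-application reading. The potential gain is much larger than the potential loss, which makes the change worthwhile without knowing r or k.

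**What to change.** Keep delta as defined. Unless 11.8 already does so, state in 11.2 and 11.8 that it is estimated from a crossover model with application, period and participant as fixed effects and the visit-specific pre-application value as a covariate acting within participant. Equivalently, take the intranasal-minus-extranasal difference in post values for each participant and regress it on sequence (coded ±1) and on the same difference in pre-application values; the intercept estimates delta. Do not use random participant effects with a single raw covariate, because its slope would mix between-person and within-person relations. Report unadjusted change as a descriptive summary.

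Name the model before results by application are examined, so that nobody chooses between adjusted and unadjusted answers afterwards across many comparisons without multiplicity correction.

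The cost is a sentence or two of wording and one degree of freedom. No new data or participants are needed. If 11.8 already specifies this model, no change is needed.

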11.3. RANDOMIZATION

Each participant will be treated with the active and control applications. The sequence of the applications will be randomly assigned using a computer-generated randomization schedule. Participants will be randomly assigned to one of two application sequences:

A. Intranasal: Extranasal

B. Extranasal: Intranasal

11.4. EVALUABILITY OF DATA

Full Analysis Set Population (FAS): The FAS population will include all participants who completed both applications.

Per protocol population (PP): The PP population is a subset of the FAS population, which did not have a major protocol deviation likely to significantly affect the primary outcome of the study. If the PP and FAS populations are exactly the same, then additional exploratory analyses on the PP population will not be performed.

Safety Population: The safety population will include all participants that initiated at least one application.

11.5. GENERAL STATISTICAL CONSIDERATIONS

Statistical analyses will use a two-tailed test and will be evaluated at an α of 0.05 unless otherwise specified. The mean, standard deviation (SD), median, minimum and maximum will be presented for continuous variables such as participant age. For categorical variables, such as sex, the number for each category, the total number evaluated, and the percentage will be presented.

The study being exploratory no correction for multiplicity will be made to the statistical comparisons.

11.6. PARTICIPANT ACCOUNTABILITY AND MISSING DATA

Participation in the study will be summarized by presenting the number of participants who were enrolled, the number of participants who only completed the first application and the number of participants who completed both applications. No imputation for missing values will be performed.

11.7. PARTICIPANT DEMOGRAPHIC AND BASELINE CHARACTERISTICS

The demographic and baseline characteristics of the study population observed will be presented descriptively.

[REDACTED]

[REDACTED]

[REDACTED]

[REDACTED]

[REDACTED]

[REDACTED]

[REDACTED]

[REDACTED]

12. FINAL CLINICAL STUDY REPORT

A final clinical study report will be prepared after completion of the study.

13. COMPLIANCE WITH GOOD CLINICAL PRACTICES, ETHICAL CONSIDERATIONS, AND ADMINISTRATIVE ISSUES

13.1. PROTECTION OF HUMAN PARTICIPANTS

13.1.1. Participant Informed Consent

Informed consent must take place before any study specific procedures are initiated. Signed and dated written informed consent must be obtained from each participant and/or from the participant's parent or legal guardian prior to enrollment into the study.

All ICFs must be approved for use by the sponsor and receive approval/favorable opinion from an Ethics Committee (EC) prior to their use. If the consent form requires revision (e.g., due to a protocol amendment or significant new safety information), it is the Investigator's responsibility to ensure that the amended informed consent is reviewed and approved by Sponsor and [REDACTED] prior to submission to the governing EC and that it is read, signed and dated by all participants subsequently enrolled in the study as well as those currently enrolled in the study.

If informed consent is taken under special circumstances (oral informed consent), then the procedures to be followed must be determined by [REDACTED] and/or study sponsor and provided in writing by [REDACTED] and/or study Sponsor prior to the consent process.

13.1.2. Ethics Committee (EC) Approval

This study is to be conducted in accordance with the harmonized EC standard *Clinical investigation of medical devices for human subjects – Good clinical practice* (EN ISO 14155). The Investigator must obtain appropriate EC approval before initiating the study and re-approval at least annually.

13.1.3. Ethical Conduct of the Study

This study will be conducted in compliance with the protocol, Good Clinical Practices (GCPs), including the International Conference on Harmonisation (ICH) Guidelines, and the ethical principles that originated with the Declaration of Helsinki.

13.1.4. Participant Confidentiality

All personal study participant data collected and processed for the purposes of this study should be maintained by the Investigator and his/her staff with adequate precautions to ensure that the confidentiality of the data is in accordance with local, state, and federal laws and regulations.

Monitors, auditors and other authorized representatives of [REDACTED] the Sponsor, the EC approving this study and the regulatory authorities will be granted direct access to the study participant's original medical and study records for verification of the data and/or clinical trial procedures.

Access to this information will be permitted to the aforementioned individuals to the extent permitted by law.

A report of the results of this study may be published or sent to the appropriate health authorities in any country in which the study device may ultimately be marketed, but the participant's identity will not be disclosed in these documents.

13.2. DOCUMENTATION

Source documents may include a participant's medical records, hospital charts, clinic charts, the Investigator's study participant files, as well as the results of diagnostic tests such as X-rays, laboratory tests, and electrocardiographs. The Investigator's copy of the CRFs serves as the Investigator's record of a participant's study-related data.

13.2.1. Retention of Documentation

All study related correspondence, participant records, consent forms, record of the distribution and use of all study device and copies of CRFs should be maintained on file for at least two years after the last approval of a marketing application in an ICH region and until there are no pending or contemplated marketing applications in an ICH region; or until at least two years have elapsed since the formal discontinuation of clinical development of the study device. These documents will be retained for a longer period if required by the applicable regulatory requirements or by an agreement with the Sponsor. It is the responsibility of the Sponsor to inform the Investigator/institution as to when these documents no longer need to be retained. On site and off site storage facilities are allocated which ensure that all stored records are identifiable and retrievable, and the storage areas are free from damp and other agents which could cause premature deterioration. All records are retained for the minimum legal requirements. For clinical records the minimum requirement is of 7 years; requirements vary for records relative to the execution of individual customer contracts.

If the responsible Investigator retires, relocates, or for other reasons withdraws from the responsibility of keeping study records, custody must be transferred to a person who will accept the responsibility. The Sponsor must be notified in writing of the name and address of the new custodian.

13.3. REGULATORY STATUS

The Allergan TrueTear device received CE Mark on December 22, 2014 (CE 615662). It has been approved for marketing in Canada and Australia as well. This device has been granted marketing authorization by the US Food and Drug Administration (FDA).

13.4. LABELING, PACKAGING, STORAGE, ACCOUNTABILITY, AND RETURN OR DISPOSAL OF STUDY DEVICE

All devices will be stored and maintained in accordance with the corresponding Instructions for Use. Used disposable devices should be discarded after use; unused disposable devices should be returned to the Sponsor at the conclusion of the study. A device accountability log will be maintained by the site and will be filed in the Trial Master File.

13.5. RECORDING OF DATA ON SOURCE DOCUMENTS AND CASE REPORT FORMS (eCRF S)

The EDC system, EntryPoint i4 is CFR21 Part 11 compliant; all participant data will be captured in the participant eCRFs (i.e. source document). The Investigator is responsible for ensuring that study data is completely and accurately recorded on each participant's eCRF and all study-related materials. EntryPoint i4 has a full data audit trail and access to the eCRF is password controlled for individual user accounts; the combined procedures ensure that all changes are time stamps and the individual who made the change identified.

13.6. AMENDMENTS TO THE PROTOCOL

Any amendment containing major modifications (particularly if it may involve an increased risk to the participants) must be approved by the EC before it may be implemented. No change in the conduct of the study can be instituted without written approval from the Sponsor.

[figure not shown]
